5.5 Noncompliance

All instances of protocol deviations will be entered into Monitor Express and will be reviewed and signed off by the Investigator and Theradex Oncology.

6.0 TREATMENT OF SUBJECTS

6.1 Drug Preparation and Administration

NBF-006 is intended for intravenous (IV) infusion use and exposure to direct sunlight should be avoided. Before use, the drug product vial is reconstituted with 5.6 mL of Acetate Diluent to bring the total constituted volume to approximately 6.7 mL, yielding a drug concentration of approximately 1.5 mg/mL. The constituted suspension is diluted into sterile saline diluent to a total volume of 300 mL (or to a total volume of 320 mL for the 1.6 mg/kg dose level) in the clinic for IV infusion to patients. The admixture solution will achieve a final desired drug concentration within acceptable physiological pH and tonicity for IV administration to patients.

NBF-006 infusion will be implemented as a stepwise infusion:

- (1) 0.5 mL/min for 10 minutes,
- (2) then 1.5 mL/min for 10 minutes, and
- (3) finally 6 mL/min for the remaining volume

Total infusion duration of approximately 70 minutes (\pm 20 minutes).

Doses ranging from 0.15 to 1.6 mg/kg will be evaluated. The drug is administered weekly for 4 weeks followed by a 2-week rest period. The length of each cycle is 6 weeks.

For detailed instructions on vial concentration, preparation, and dispensing, please refer to the Pharmacy Manual.

The target infusion time is 70 minutes, but infusion rate will be adjusted as needed (e.g., due to infusion reaction). Premedication with H1/H2 antagonists should be considered if infusion reactions occur; refer to the management of infusion-related reactions (IRRs) outlined in Section [8.1.2.8](#).

The reconstituted drug (NBF-006 in Acetate Diluent) is stable in the glass vial for 2 hours at ambient conditions. The reconstituted drug solution is further diluted to the appropriate dose concentration with saline into a DEHP-free IV bag; this IV infusion solution is stable for 4 hours at ambient conditions. The drug product (lyophilized form, reconstituted solution, and IV infusion solution) should be kept out of direct sunlight.

Both NBF-006 and the Acetate Diluent will be provided by the Sponsor. Ordering instructions will be provided.

6.1.1 Dose Escalation Scheme

Part A (Dose escalation; Table 1):

NBF-006 (300 mL, or 320 mL for the 1.6 mg/kg dose level) will be administered via IV infusion over 70 minutes, QW for 4 weeks followed by a 2-week rest period. The length of each cycle is 6 weeks. Patients in dose levels 1-4 (0.15 mg/kg, 0.3 mg/kg, 0.6 mg/kg, and 1.2 mg/kg) of Part A, will have previously treated progressive or metastatic NSCLC, pancreatic, or colorectal cancer, regardless of KRAS mutation status. Patients in dose level 5 (1.6 mg/kg) of Part A must have previously treated progressive or metastatic NSCLC with confirmed KRAS mutation.

The first dose level (0.15 mg/kg) will be a single patient cohort. If any Grade 2 or greater drug-related event occurs during the first cycle of treatment, the cohort will be expanded up to 3 patients. If a DLT occurs during the first cycle, the cohort will be expanded up to 6 patients before proceeding with dose escalation.

Subsequent cohorts in the dose escalation phase will enroll patients following the standard 3+3 design. If 1 out of 3 patients experience a DLT during the first cycle of treatment, the dose cohort will be expanded up to 6 patients. If no DLT is observed in the first 3 patients enrolled at the highest dose, this cohort will be expanded to 6 patients. If 2 or more out of 6 patients experience DLTs, the MTD has been exceeded, and dose escalation will cease. Up to 3 additional patients will be enrolled at a lower dose if only 3 patients were treated at that dose level, to confirm safety of that dose. MTD will be defined as a dose where 0 or 1 out of 6 patients have DLTs. To collect clinically important information in the target population, and prepare for Part B, the 6-patient cohort(s) must each include at least 3 patients with histologically or cytologically confirmed progressive or metastatic NSCLC, up to dose level 4 (1.2 mg/kg). In dose level 5 (1.6 mg/kg), only patients with previously-treated NSCLC with KRAS mutation will be included. Once safety has been confirmed in Part A at 1.6 mg/kg (i.e. 0-1 DLT in 6 patients), an additional 4 patients with KRAS-mutated NSCLC will be enrolled in Part B of the study at this dose level. Stratification for GSTT1-null genotype patients will not occur in Part A, but whole blood samples will still be collected during the screening visit for Part A dose level 5 (1.6 mg/kg) and batch analyzed at a central lab.

One dose de-escalation is permitted.

Table 1: Part A NBF-006 Dose Levels

Dose level	NBF-006 dose	Number of patients
1	0.15 mg/kg	1-6
2	0.3 mg/kg	3-6
3	0.6 mg/kg	3-6
4	1.2 mg/kg	3-6
5	1.6 mg/kg	3-6

6.1.2 Part B (Dose Expansion)

After MTD is confirmed in Part A for up to dose level 4 (1.2 mg/kg), enrollment in Part B may commence. Part B will enroll patients with previously treated progressive or metastatic NSCLC with confirmed KRAS mutation.

The two dose levels that will be explored further in Part B are 0.6 mg/kg and 1.2 mg/kg. Twenty patients will be enrolled in Part B, with 10 patients enrolled in each of the two cohorts. Both cohorts will be stratified for GSTT1-null genotype patients to ensure equal allocation to the cohorts with different doses. Once dose level 5 (1.6 mg/kg) has been confirmed to be safe in Part A, an additional 4 patients will be enrolled at dose level 1.6 mg/kg, for a planned total of 24 patients in Part B. This last dose level in Part B at 1.6 mg/kg will also be stratified for GSTT1-null genotype patients to be balanced with the previous two expansion cohorts as much as possible. The final proportion of GSTT1-null patients treated at the highest dose level may depend on the first 6 patients treated in Part A (not stratified).

Table 2: Part B NBF-006 Dose Levels

Dose level	NBF-006 dose	Number of patients
3	0.6 mg/kg	10
4	1.2 mg/kg	10
5	1.6 mg/kg	4*

*Dose level 5 pending confirmation of safety in Part A

NBF-006 will be administered by weekly infusion for 4 consecutive weeks of a 6-week cycle.

6.1.3 Dose-Limiting Toxicity (Part A)

AEs will be assessed per National Cancer Institute (NCI) Common Terminology Criteria (CTCAE) version 5.0. DLT is defined as any treatment related toxicity (i.e., not attributable to the underlying active disease, or intercurrent illness) during the first 42 days (Cycle 1) of study treatment meeting any of the criteria described below. Ongoing safety events beyond

Cycle 1 will be reviewed across all cohorts during the study to help inform dose escalation decisions. Note, that all patients who enrolled in the study, regardless of their replacement as per Section 5.4.2, will be included in assessment of DLT.

DLT includes:

1. Treatment-related hematological toxicities as follows:
 - Grade 4 neutropenia.
 - Any grade neutropenic fever.
 - \geq Grade 3 thrombocytopenia lasting longer than 3 consecutive days.
 - \geq Grade 3 thrombocytopenia with bleeding.
 - Any other confirmed hematological toxicity \geq Grade 4 (a repeat test may be required for confirmation of an isolated abnormality in the absence of clinical signs, symptoms or other abnormal investigations, i.e., a suspected spurious value).
2. Treatment-related non-hematological toxicity \geq Grade 3 including:
 - Electrolyte abnormalities that do not resolve within 48 hours of intervention (a repeat test may be required for confirmation of an isolated abnormality in the absence of clinical signs, symptoms or other abnormal investigations, i.e., a suspected spurious value).
 - \geq Grade 3 IRRs.
 - \geq Grade 3 cytokine release syndrome.
 - Any hepatic toxicity meeting Hy's Law criteria.
 - Grade 3 nausea/vomiting or diarrhea or other self-limited or medically controllable toxicities that last $>$ 72 hours regardless of medical intervention.
3. Any other treatment-related toxicity, i.e., greater than at baseline, which is clinically significant and/or unacceptable, does not respond to supportive care and results in a disruption of the dosing schedule of more than 14 days.
4. Any death not clearly due to the underlying disease or extraneous causes.

DLT excludes:

- Alopecia of any grade.

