7.3.1.4 Week 4 (Day 22 ± 3)

- Vital signs
- ECG
- Hematology
- Blood chemistry
- PK blood sampling (pre- and post-dose)
- NBF-006 administration
- Concomitant medications
- AEs
- Optional biopsy 24 (±3) hours after completion of the 4th dose in cycle 1.

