7.3.1.5 Weeks 5 (Day 29-35)

Rest

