7.3.1.6 Week 6 (Day 36-42)

- Tumor measurement (use same method as baseline) performed at the end of every even cycle for Part A dose levels 1-4 and performed at the end of every cycle for Part A dose level 5 and all patients in Part B.

7.3.2 Cycle 2

7.3.2.1 Week 1 (Day 1 should occur within 3 days of Day 42 of previous cycle)

- Physical Exam
- Weight

- Vital signs
- ECOG
- Hematology
- Blood chemistry
- Urinalysis
- Pregnancy test
- ADA assay sampling (pre-dose)
- PK blood sampling (pre-dose)
- NBF-006 administration
- Concomitant medications
- AEs

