7.3.3.6 Week 6 (Day 36-42)

- Tumor measurement (use same method as baseline) performed at the end of every even cycle for Part A dose levels 1-4 and performed at the end of every cycle for Part A dose level 5 and all patients in Part B.

7.4 End of Treatment (to be performed within 30 ± 3 days after last treatment)

The following assessments will be performed for all patients who are terminating treatment due to any reason. The End of Treatment (EOT) visit should be performed immediately after the patient discontinues treatment and should be no later than 30 ± 3 days after the last dose.

- Physical Exam
- Weight
- Vital signs
- ECG
- ECOG
- Tumor measurement (use same method as baseline)
- Hematology
- Blood chemistry
- Urinalysis
- Pregnancy test
- ADA assay sampling
- Concomitant medications
- AEs

7.5 30 Day Safety Follow up Visit (±3)

- Physical Exam
- Weight
- ECOG
- Hematology
- Blood chemistry
- Urinalysis

- ADA assay sampling
- AEs

If the EOT visit is performed 30 ± 3 days after the last dosing, the safety follow-up visit can be omitted.

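### Between the Day 22 visit and Cycle 2 Day 1 no haematology or chemistry is scheduled, so the laboratory part of the 42-day DLT window is not fully covered

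*Protocol*

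**What the plan says.** **The window.** Section 6.1.3 defines a DLT as a treatment-related toxicity "during the first 42 days (Cycle 1) of study treatment meeting any of the criteria described below". Some of the listed criteria need no symptom: Grade 4 neutropenia, Grade 3 or higher thrombocytopenia lasting more than 3 days, other confirmed Grade 4 haematological toxicity, and hepatic toxicity meeting Hy's Law.

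**The laboratory schedule.** Tables 3 and 4 and sections 7.3.1.1 to 7.3.1.4 place Cycle 1 haematology and chemistry on Days 1, 8, 15 and 22 (the last three ± 3 days). Section 7.3.1.5 makes Week 5 a rest week with no assessment. Section 7.3.1.6 lists only tumour measurement for Week 6. Haematology and chemistry return in section 7.3.2.1, where Cycle 2 "Day 1 should occur within 3 days of Day 42 of previous cycle". For patients who stop, section 7.4 includes both panels at an end-of-treatment visit that "should be no later than 30 ± 3 days after the last dose".

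**The use made of the count.** The number of patients with DLTs is part of the Part A primary endpoint (9.2.1). The MTD rests on first-cycle safety data and DLTs (6.1.4). A finding of 0-1 DLT in 6 patients at 1.6 mg/kg opens the Part B cohort at that dose (6.1.1).

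**The concern.** The endpoint is defined over 42 days, but its laboratory component is scheduled over roughly the first 22. The uncovered stretch follows the fourth dose, when cumulative exposure within the cycle is greatest. A neutrophil or platelet nadir, or a rise in transaminases and bilirubin, that causes no symptoms and recovers before the next draw would leave no record.

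The criterion that depends on duration is harder still to apply there: without a first abnormal platelet count, nothing prompts the repeat counts needed to show that it lasted more than 3 days.

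The status of a late finding is also unclear. Read literally, an abnormality first seen on nominal Day 43 misses the window by one day.

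Both effects point the same way, towards a lower DLT count and an easier pass. With a decision rule on six patients, one uncounted event can change the result.

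**Working it through.** The protocol makes no sample size calculation (9.6) and gives no DLT rate, so there is no figure of its own to reproduce. The check is a day count followed by two illustrations.

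**1. Day count** (inputs: 6.1.3, 7.3.1.4, 7.3.2.1, 7.4)

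- Nominal gap inside the window: Days 23-42, so 42 − 22 = 20 days, and 20/42 = 48%.
- With the ± 3 days on Day 22: 42 − 25 = 17 to 42 − 19 = 23 days.
- Cycle 2 Day 1 within 3 days of Day 42: Day 39 to Day 45. With Day 22 on schedule and Cycle 2 Day 1 on Day 39, the untested days are 23-38, which is 16 days, and that draw lies inside the window.
- Interval from the last Cycle 1 draw to the next: nominally 43 − 22 = 21 days, ranging from 39 − 25 = 14 to 45 − 19 = 26.
- End of treatment after a last dose on Day 22: as late as 22 + 30 = Day 52, ± 3.

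**2. How much would the next draw catch?** Assumption: onset is equally likely on each of Days 23-42, and the abnormality lasts L days. It is still present on Day 43 if onset falls between Day 44 − L and Day 42. That is L − 1 of 20 possible days.

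| L (days) | Still present on Day 43 |
|---|---|
| 3 | 2/20 = 10% |
| 7 | 6/20 = 30% |
| 10 | 9/20 = 45% |
| 14 | 13/20 = 65% |

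For L = 7 the share is 35% with a draw on Day 39 and 20% with one on Day 45.

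**3. Effect on the 0-1 of 6 rule.** With true DLT rate p, the chance of passing is (1 − p)^6 + 6p(1 − p)^5. If a share f of DLTs goes uncounted, p is replaced by p(1 − f). Both p and f are assumptions.

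| p | f = 0 | f = 0.10 | f = 0.25 | f = 0.50 |
|---|---|---|---|---|
| 0.20 | 0.655 | 0.704 | 0.776 | 0.886 |
| 0.33 | 0.358 | 0.427 | 0.540 | 0.741 |
| 0.50 | 0.109 | 0.164 | 0.274 | 0.534 |

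Example at p = 0.33, f = 0: 0.67^6 + 6(0.33)(0.67^5) = 0.090 + 0.267 = 0.358. Enumerating the path of three patients and then three more gives the same value.

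The table shows the direction and sensitivity of the rule. It does not estimate the bias in this trial.

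**The case against.** The strongest reply is that weekly bloods in dosing weeks, none in rest weeks and a check before the next cycle is a deliberate monitoring choice, and that little is lost by it. Several parts of that reply stand.

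- **Testing resumes.** A reader might infer that every laboratory DLT after the fourth dose goes unseen. The documents do not support this. Cycle 2 Day 1 may fall on Days 39-42, inside the window, and persistent abnormalities would be found there. End-of-treatment bloods are meant to be taken promptly after stopping, although they may be late.
- **The Day 22 draw is not stated to be pre-dose.** Section 7.3.1.4 gives a timing for PK ("PK blood sampling (pre- and post-dose") but none for haematology and chemistry. One cannot assert from the text that no scheduled sample follows the fourth dose. Even so, a same-day sample would not show an effect that develops over later days.
- **Clinical events surface.** AEs are recorded throughout, so neutropenic fever or bleeding would be noticed, and unscheduled tests are not barred.
- **The electrolyte criterion does not belong on the list.** It requires failure to resolve within 48 hours of intervention, which an undetected, untreated abnormality cannot meet.
- **The decision uses more than the count.** Section 6.1.3 lets events after Cycle 1 inform escalation, 6.1.4 refers to safety data as well as DLTs, and 8.1.2.10 gives the decisions to the Safety Review Committee. A Day 43 finding is not lost to that committee.
- **Existing experience is reassuring.** Section 2.4 reports no DLTs and no treatment-related Grade 3-4 events in 14 patients at dose levels 1-4, and section 2.3.4 describes minimal haematology and chemistry changes in the repeat-dose animal studies. The clinical record is itself limited by whatever laboratory schedule produced it.

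None of this closes the gap for a silent, transient abnormality, and none of it gives a Day 43 result a defined place in the 0-1 of 6 count.

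**Conclusion.** The point holds in a limited form. The DLT window and the Cycle 1 laboratory schedule do not match, and following the plan as written can undercount the Part A primary endpoint. What can be missed is narrow: Grade 4 neutropenia, Grade 3 or higher thrombocytopenia lasting more than 3 days, or a Hy's Law pattern, where it causes no symptoms, begins after the fourth dose and resolves before the next draw. Separately, an abnormality first found on nominal Day 43 is excluded on a literal reading.

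The nominal gap is 20 of 42 days, 17-23 with the Day 22 window, and shorter if Cycle 2 Day 1 falls early. The direction of bias is downward. Its size cannot be stated, because the pass probabilities above rest entirely on assumed values of p and f.

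A reader might take this as a defect particular to 1.6 mg/kg. It is not: the schedule is common to all Part A dose levels, and Table 4 repeats it for Part B, where 9.2.1 also names DLTs among the safety endpoints. The 1.6 mg/kg decision matters most because dose levels 1-4 have already been evaluated (2.4). This is a cheap and worthwhile repair, and no ground for saying that the escalation decisions are invalid.

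**What to change.** Reconcile 6.1.3 with Tables 3 and 4 and with 7.3.1.4 to 7.3.1.6, so that laboratory ascertainment covers the stated window.

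1. In 6.1.3, state whether bloods drawn before dosing on Cycle 2 Day 1, or end-of-treatment bloods if Cycle 2 is not started, belong to the Cycle 1 DLT assessment. A Day 43 result should not be excluded by one day through silence in the text.
2. Add haematology and chemistry to contacts that already exist after the Day 22 infusion: a post-dose PK draw (8.3 runs these to 72 hours in Part A and 24 hours in Part B), and the Week 6 tumour assessment where it takes place at the clinic. In Cycle 1 that assessment applies to dose level 5 and Part B only.
3. State whether the Day 22 haematology and chemistry are drawn before or after the infusion.

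**Cost.** An amendment to these sections and tables, one or two routine panels per patient, and possibly slightly more counted DLTs. The first and third items need wording only.

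**Limits.** Coverage would still be incomplete: a 72-hour draw falls at about Day 25, so roughly Days 26-35 would remain without a scheduled test. Single draws cannot by themselves show a platelet abnormality lasting more than 3 days, but they supply the first abnormal value that prompts a repeat.

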6.1.4 Maximum Tolerated Dose (Part A)

The definition of MTD will be based upon review of safety data and DLTs corresponding to the first cycle of therapy in at least 6 evaluable patients. MTD will be defined as a dose where 0 or 1 out of 6 patients have DLTs.

6.2 Dose Interruptions/Withholding for Infusion Reactions or Other Reasons

Guidelines for management of IRRs, including circumstances for interrupting or

discontinuing dosing, are in Section 8.1.2.8.

Study drug may be withheld from a patient based on the Investigator's decision in the event of intercurrent illness, AEs, administrative reasons, or other reasons. If the patient's condition subsequently improves, or the situation that resulted in withholding study drug rectifies itself, the Investigator may resume dosing on the next practical dosing day.

Do not "make up" for missed or skipped doses i.e. if Week 3 dose is missed, do not administer a dose during the rest period (Week 5 or 6). Patients who miss a dose during Cycle 1 may be replaced per Section 5.4.2. The interruption and/or missed dose(s) should be recorded.

6.3 Concomitant Treatment

Patients must not receive any other concurrent anti-cancer therapy, including investigational agents (with exception of the Acetate Diluent), chemotherapy, immunotherapy, hormonal, or biologic therapies while on study treatment. Palliative radiotherapy is allowed as medically indicated after completion of the first treatment cycle, and after discussion with medical monitor.

Supportive treatment may include anti-emetic, anti-diarrheal, anti-pyretic, anti-histamines, analgesics, antibiotics, and blood products. Treatment with denosumab or bisphosphonates, to prevent skeletal-related events in patients with bone metastases, is allowed throughout the trial.

At the discretion of the treating physician, patients may receive anti-histamine prophylaxis according to the standard of care (SOC) in clinical practice.

In case of IRRs, patients may be pretreated as needed with an H1 antagonist (e.g., diphenhydramine, hydroxyzine, or chlorpheniramine) and an H2 antagonist (e.g., famotidine) dosed in accordance with approved labelling or SOC. If premedication is administered parenterally, it should be given within 30 minutes of the start of infusion (SOI); if premedication is given orally, it should be given 60-90 minutes prior to SOI.

6.4 Monitoring Subject Compliance

This study will be monitored by Nitto BioPharma, Inc. or its Contract Research Organization (Theradex Oncology) according to ICH E6 guidelines of GCP. The study site monitor will regularly visit the study sites to ensure that the study is conducted according to the protocol and GCP principles.

7.0 STUDY EVALUATIONS

7.1 Schedule of Study Evaluations

Study evaluations for Part A and Part B are summarized in [Table 3](#) and [Table 4](#), respectively, and described in Sections [0](#) through [7.5](#).

Table 3: Study Calendar (Part A)

Part A Evaluations	Pre-treatment ^a	Cycle 1						Cycle 2						Cycle 3 & beyond				EOT	30-day safety FU visit (±3)	
		Wk 1 D1	Wk 2 D8 ±3	Wk 3 D15 ±3	Wk 4 D22 ±3	Wk 5 D29-35	Wk 6 D36-42	Wk 1 D1	Wk 2 D8 ±3	Wk 3 D15 ±3	Wk 4 D22 ±3	Wk 5 D29-35	Wk 6 D36-42	Wk 1 D1	Wk 2 Wk 3 Wk 4	Wk 5	Wk 6			
Informed consent (incl. optional biopsy consent)	X																			
Medical history	X																			
Physical exam	X	X ^b						X						X					X	X
Weight	X	X ^b						X						X					X	X
Vital signs ^e	X	X ^b	X	X	X			X	X	X	X			X					X	
ECG ^f	X	X ^b			X														X	
ECOG performance status	X	X ^b						X						X					X	X
Tumor measurement ^g (tumor markers, if applicable)	X						X						X				X		X	
Hematology ^h	X	X ^b	X	X	X			X	X	X	X			X					X	X
Blood chemistry ⁱ	X	X ^b	X	X	X			X	X	X	X			X					X	X
Urinalysis	X	X ^b						X						X					X	X
Blood sample for immune activation biomarkers ^j		X																		
Pregnancy test	X ^k							X						X					X	
Blood sample for ADA assay ^c		X		X				X						X					X	X
PK blood sampling ^d		X	X		X			X												
Blood sample for exploratory biomarkers	X																			
Blood sample for GSTP KD ⁿ		X	X																	
Confirmation of KRAS mutation ^l (dose levels 1-4 optional; dose level 5 mandatory)	X																			
GSTT1 genotyping ^p	X																			
Optional biopsy ^o	X				X															
NBF-006 administration ^m		X	X	X	X			X	X	X	X			X	X					
Concomitant medications	X	<----- throughout study ----->																X		

Adverse events	<----- throughout study ----->	X	X

a: Screening assessments may be performed within 28 days of study to treatment initiation, unless specified.
 
b: For Cycle 1 Day 1, these tests may be performed within 3 days prior to Cycle 1 Day 1. Physical exam and pre-treatment tests done within 3 days of Cycle 1 Day 1 do not need to be repeated for Wk1D1 unless clinically indicated.
 
c: ADA assay timepoints:
 
 • Cycle 1, Day 1: pre-dose • Cycle 1, Day 15: pre-dose • Cycle 2, Cycle 4, Cycle 6, Cycle 8, etc. (i.e., every even numbered cycle), up to one year: Day 1 pre-dose • Year 2 and beyond: every 6 months • EOT • 30-day safety follow up visit 
d: PK timepoints:
 
 • Cycle 1, Day 1: 
 • Before start of infusion (SOI), • During the infusion: 20 m (±5min) after the start of the last infusion step implemented at 6 mL/min rate • End of Infusion (EOI); after EOI: 0.5 hr (±5min), 2 hr (±10min), 6 hr (±15min), 24 hr (±1hr), 48 hr (±2hr), 72 hr (±3hr) • Cycle 1, Day 8: pre-dose • Cycle 1, Day 22: 
 • Before SOI • During the infusion: 20 min (±5min) after the start of the last infusion step implemented at 6 mL/min rate • End of Infusion (EOI); after EOI: 0.5 hr (±5min), 2 hr (±10min), 6 hr (±15min), 24 hr (±1hr), 48 hr (±2hr), 72 hr (±3hr) • Cycle 2, Day 1: pre-dose 
e: Vital signs, including blood pressure, heart rate, respiration rate, and temperature. During Cycle 1: Before SOI, EOI; after EOI: 1hr (±5min), 2hr (±10min). Other days: only before SOI and EOI.
 
f: Standard 12-lead ECG (in triplicate) while patient is in semi-recumbent position. Perform at screening, Cycle 1 First and fourth doses: within 15 minutes prior to SOI, then 15 min (±5min), 30 min (±10min), 1 hr (±10min) (at EOI)
 
g: Tumor measurement by RECIST version 1.1 and tumor markers will be collected at baseline and at the end of every even numbered cycle in Part A, dose levels 1-4 (0.15 mg/kg, 0.3 mg/kg, 0.6 mg/kg, 1.2 mg/kg) and at the end of every cycle for dose level 5 (1.6 mg/kg), if applicable; the same method used at baseline for a patient should be used consistently for all evaluations throughout the study. To be assigned a status of PR or CR, changes in tumor measurements must be confirmed by repeat assessments that should be performed at 4 weeks but no later than 5 weeks for patients in dose levels 1-4 (0.15 mg/kg, 0.3 mg/kg, 0.6 mg/kg, and 1.2 mg/kg) in Part A after the criteria for response are first met. Response will be confirmed at 4 weeks or at the next scheduled scan (at Week 6 of the following cycle) for patients in dose level 5 (1.6 mg/kg) in Part A. If a confirmative scan is done after 4 weeks, the next scheduled scan at Week 6 of the following cycle may be omitted. In the case of SD, follow-up measurements must have met the SD criteria at least once after study entry at a minimum interval of 5 weeks.
 
h: Hematology, including hemoglobin, white blood cell with differential, and platelet count.
 
i: Blood chemistry, including sodium, potassium, blood urea nitrogen, glucose, SGOT/SGPT (ALT/AST), alkaline phosphatase, total protein, total bilirubin, albumin, creatinine, and calcium.
 
j: Blood samples collected during Cycle 1 (Week 1) for all patients treated in Part A of the study for determination of complement (CH50, Bb, C3a, C5a) and cytokines (IFN-γ, IL-1β, IL-6, TNF-α):
 
 • Pre-dose • 10 ± 3 minutes after SOI • 60 ± 10 minutes after EOI 			

- 6 hr ± 15 minutes after EOI
 - 24 hr ± 1 hr after EOI
- k: Pregnancy test; for women of childbearing potential, a negative pregnancy test (urine or serum) must be done within 7 days prior to study treatment initiation and documented.
- l: Confirmation of KRAS mutation: optional for Part A dose levels 1-4 and mandatory for Part A dose level 5 (1.6 mg/kg). Obtain archive sample if available; otherwise, a fresh biopsy (low or minimal risk only) is required. If such type of biopsy is needed but cannot feasibly be collected, the Sponsor and Medical Monitor should be consulted. Genomic tumor profile report is acceptable in lieu of a biopsy. **Note:** if at any time during the trial a biopsy is performed as part of routine medical care, we may request a sample.
- m: NBF-006 is administered IV QC (minimum 4 days apart) preferably on a Monday or Tuesday (to accommodate the PK schedule) during Cycle 1.
- n: GSTP KD time points collected in the 6 patients from Part A at dose level 5 (1.6 mg/kg):
- Cycle 1, Day 1:
 - Before SOI
 - After EOI: 6 hr (±15min), 24 hr (±1hr)
 - Cycle 1, Day 8: before SOI
- o: Optional biopsy collected during screening and 24 (±3) hours after the 4th dose in cycle 1. Only for patients signing the optional biopsy consent, and when the biopsy can be safely obtained.
- p: In Part A of the study, patients will not be stratified for the GSTT1- null genotype, but whole blood samples will still be collected during the screening visit and batch-analyzed at a central laboratory.
- Note: Each patient must remain in clinic for a 6-hour safety observation period after each NBF-006 infusion, until the safety review committee has reviewed a 3-patient cohort and recommended a reduced observation time at that dose level. Please see Section [8.1.2.8](#) for details.

Table 4: Study Calendar (Part B)

Part B Evaluations	Pre-treatment ^a	Cycle 1						Cycle 2						Cycle 3 & beyond				EOT	30-day safety FU visit (±3)
		Wk 1 D1	Wk 2 D8 ±3	Wk 3 D15 ±3	Wk 4 D22 ±3	Wk 5 D29-35	Wk 6 D36-42	Wk 1 D1	Wk 2 D8 ±3	Wk 3 D15 ±3	Wk 4 D22 ±3	Wk 5 D29-35	Wk 6 D36-42	Wk 1 D1	Wk 2 Wk 3 Wk 4	Wk 5	Wk 6		
Informed consent (incl. optional biopsy consent)	X																		
Medical history	X																		
Physical exam	X	X ^b						X						X				X	X
Weight	X	X ^b						X						X				X	X
Vital signs ^e	X	X ^b	X	X	X			X	X	X	X			X				X	
ECG ^f	X	X ^b			X													X	
ECOG performance status	X	X ^b						X						X				X	X
Tumor measurement ^g (tumor markers, if applicable)	X						X					X					X	X	
Hematology ^h	X	X ^b	X	X	X			X	X	X	X			X				X	X
Blood chemistry ⁱ	X	X ^b	X	X	X			X	X	X	X			X				X	X
Urinalysis	X	X ^b						X						X				X	X
Blood sample for immune activation biomarkers ^j		X																	
Pregnancy test	X ^k							X						X				X	
Blood sample for ADA assay ^c		X		X				X						X				X	X
PK blood sampling ^d		X	X		X			X											
Blood sample for exploratory biomarkers	X																		
Blood sample for GSTP KD ⁿ		X	X																
Confirmation of KRAS mutation ^l (Part B mandatory)	X																		
GSTT1 genotyping ^p	X																		
Optional biopsy ^o	X				X														
NBF-006 administration ^m		X	X	X	X			X	X	X	X			X	X				
Concomitant medications	X	----- throughout study -----															X		
Adverse events		----- throughout study -----															X	X	

- a: Screening assessments may be performed within 28 days of study to treatment initiation, unless specified.
- b: For Cycle 1 Day 1, these tests may be performed within 3 days prior to Cycle 1 Day 1. Physical exam and pre-treatment tests done within 3 days of Cycle 1 Day 1 do not need to be repeated for Wk1D1 unless clinically indicated.
- c: ADA assay timepoints:
- Cycle 1, Day 1: pre-dose
 - Cycle 1, Day 15: pre-dose
 - Cycle 2, Cycle 4, Cycle 6, Cycle 8, etc. (i.e., every even numbered cycle), up to one year: Day 1 pre-dose
 - Year 2 and beyond: every 6 months
 - EOTs
 - 30-day safety follow up visit
- d: PK timepoints:
- Cycle 1, Day 1:
 - Before start of infusion (SOI),
 - During the infusion: 20 m (± 5 min) after the start of the last infusion step implemented at 6 mL/min rate
 - End of Infusion (EOI); after EOI: 0.5 hr (± 5 min), 2 hr (± 10 min), 6 hr (± 15 min), 24 hr (± 1 hr)
 - Cycle 1, Day 8: pre-dose
 - Cycle 1, Day 22:
 - Before SOI
 - During the infusion: 20 m (± 5 min) after the start of the last infusion step implemented at 6 mL/min rate
 - End of Infusion (EOI); after EOI: 0.5 hr (± 5 min), 2 hr (± 10 min), 6 hr (± 15 min), 24 hr (± 1 hr)
 - Cycle 2, Day 1: pre-dose
- e: Vital signs, including blood pressure, heart rate, respiration rate, and temperature. During Cycle 1: Before SOI, EOI; after EOI: 1hr (± 5 min), 2hr (± 10 min). Other days: only before SOI and EOI.
- f: Standard 12-lead ECG (in triplicate) while patient is in semi-recumbent position. Perform at screening, Cycle 1 First and fourth doses: within 15 minutes prior to SOI, then 15 min (± 5 min), 30 min (± 10 min), 1 hr (± 10 min) (at EOI)
- g: Tumor measurement by RECIST version 1.1 and tumor markers will be measured at baseline and at the end every cycle, if applicable; the same method used at baseline for a patient should be used consistently for all evaluations throughout the study. To be assigned a status of PR or CR, changes in tumor measurements must be confirmed at 4 weeks or at the next scheduled scan (at Week 6 of the following cycle). If a confirmative scan is done after 4 weeks, the next scheduled scan at Week 6 of the following cycle may be omitted. In the case of SD, follow-up measurements must have met the SD criteria at least once after study entry at a minimum interval of 5 weeks.
- h: Hematology, including hemoglobin, white blood cell with differential, and platelet count.
- i: Blood chemistry, including sodium, potassium, blood urea nitrogen, glucose, SGOT/SGPT (ALT/AST), alkaline phosphatase, total protein, total bilirubin, albumin, creatinine, and calcium.
- j: Blood samples collected during Cycle 1 (Week 1) for all patients treated in Part B of the study for determination of complement (CH50, Bb, C3a, C5a):
- Pre-dose
 - 10 \pm 3 minutes after SOI
 - 60 \pm 10 minutes after EOI
 - 6 hr \pm 15 minutes after EOI
 - 24 hr \pm 1 hr after EOI
- Dose levels 3 (0.6 mg/kg) and 4 (1.2 mg/kg) did not result in immune activation in Part A and therefore, cytokine activity will not be monitored at those two dose levels in Part B. However if a patient, during or after any infusion of NBF-006, develops IRR symptoms (e.g. backache, fever, nausea, headache, rash, rapid heartbeat, low blood pressure, or trouble breathing), best attempts should be made to collect cytokines as described for Part A with the exception of 10 \pm 3 minutes after SOI, which should be collected as close as feasible

to the IRR. If there is no meaningful cytokine induction in the 6-patient dose level 5 (1.6 mg/kg) during Part A, then cytokine testing will also not be needed in the remaining 4 patients at that same dose level (1.6 mg/kg), unless there are symptoms of IRR. **However, complement samples will continue to be collected for all patients.**

- k: Pregnancy test; for women of childbearing potential, a negative pregnancy test (urine or serum) must be done within 7 days prior to study treatment initiation and documented.
- l: Confirmation of KRAS mutation required for Part B. Obtain archive sample if available; otherwise, a fresh biopsy (low or minimal risk only) is required. If such type of biopsy is needed but cannot feasibly be collected, the sponsor and Medical Monitor should be consulted. Genomic tumor profile report is acceptable in lieu of a biopsy. **Note:** if at any time during the trial a biopsy is performed as part of routine medical care, we may request a sample.
- m: NBF-006 is administered IV QC (minimum 4 days apart) preferably on a Monday or Tuesday (to accommodate the PK schedule) during Cycle 1.
- n: GSTP mRNA KD time points:
 - Cycle 1, Day 1:
 - Before SOI
 - After EOI: 6 hr (± 15 min), 24 hr (± 1 hr)
 - Cycle 1, Day 8: before SOI
- o: Optional biopsy collected during screening and 24 (± 3) hours after the 4th dose in cycle 1. Only for patients signing the optional biopsy consent, and when the biopsy can be safely obtained.
- p: In Part B of the study, patients will be stratified for the GSTT1- null genotype. Analysis will be done at a central lab from blood samples collected during the screening visit. Initial patients may be enrolled before the GSTT1 status is known.

Note: Each patient must remain in clinic for a 6-hour safety observation period after the first dose, 2 hours after EOI for remaining doses in Cycle 1. The observation period may be further reduced to 30 minutes starting Cycle 2, after Medical Monitor and Investigator safety review. Please see Section [8.1.2.8](#) for details.

